9.0 Efficacy Analysis

9.1 General Considerations

There are three sets of planned efficacy analysis: analysis for the primary and key secondary endpoints (at Week 12 or Week 24), additional efficacy analysis for Period 1, and long-term efficacy analysis (Period 1 and Period 2 combined). All efficacy analyses will be carried out using the FAS population. For the Japan sub-study, efficacy analyses will be conducted for selected variables.

Period 1 Efficacy Analysis

This includes analysis for the primary and key secondary endpoints (at Week 12 or Week 24), and additional efficacy analysis for Period 1.

Standard efficacy analysis by randomized treatment groups (MTX, Upadacitinib 15 mg QD monotherapy, Upadacitinib 30 mg QD monotherapy, and additionally Upadacitinib 7.5 mg QD monotherapy for Japan sub-study only) will be performed on efficacy data up to Week 12. No protocol-defined background rescue medication or rescue switching will occur prior to the time point.

For visits at Weeks 16, 20, 24 subjects may have initiated background rescue medication due to lack of efficacy as evaluated by joint count criteria (i.e., not achieving 20%

improvement in both TJC and SJC compared with baseline at two consecutive visits). In addition, at Week 26 subjects may have switched to Upadacitinib + MTX combo treatment (rescue switching) that is different from their originally randomized treatment due to lack of efficacy as evaluated by CDAI and joint count criteria, jointly. For treatment group comparisons beyond Week 12 to the end of Period 1, appropriate approaches will be applied to assessments that occur after the time of such background rescue or rescue switching. For Week 24 reporting, this set of analyses will be presented up to Week 24.

Long Term Efficacy Analysis

Long term efficacy analysis (Period 1 and Period 2 combined) will be performed on As Observed data (defined in Section 9.1.1) by the treatment group sequences as described below. The treatment group sequences are grouped into "non-switchers" and "switchers" based on the protocol defined rescue at Week 26 (from MTX or upadacitinib to upadacitinib plus MTX).

"Non-switcher" sequences:

1. MTX
2. Upadacitinib 15 mg QD
3. Upadacitinib 30 mg QD

"Switcher" sequences:

4. MTX → Upadacitinib 15 mg QD + MTX
5. MTX → Upadacitinib 30 mg QD + MTX
6. Upadacitinib 15 mg QD → Upadacitinib 15 mg QD + MTX
7. Upadacitinib 30 mg QD → Upadacitinib 30 mg QD + MTX

For Japan sub-study, there are three additional treatment sequences:

8. Upadacitinib 7.5 mg QD
9. MTX → Upadacitinib 7.5 mg QD + MTX
10. Upadacitinib 7.5 mg QD → Upadacitinib 7.5 mg QD + MTX

There will be no statistical testing; only descriptive statistics and confidence intervals will be provided. For Week 24 reporting, this set of analyses will be presented up to Week 48.

Starting with Amendment 5.01.01 (for Japan) and Amendment 6 (for global), subjects receiving upadacitinib 30 mg QD will be switched to upadacitinib 15 mg QD. For long term efficacy analysis, subjects will continue to be summarized under the treatment sequences as described above, regardless of dose switch – i.e., for treatment sequences 3, 5 and 7, data collected after dose switch will continue to be summarized under the same treatment sequences. The visit at which dose switch occurs could be different for each subject. The first and last visits at which dose switch occurs will be noted in the summary.

Global Analysis versus Japan Sub-Study

The primary and key secondary endpoints and the subsequent multiplicity control are only applicable for global analysis for subjects randomized to MTX, Upadacitinib 15 mg QD and Upadacitinib 30 mg QD - they do not apply to Japan sub-study.

For Japan sub-study, no multiplicity adjustments will be applied and only nominal p-values will be provided for all efficacy analyses. In addition, model adjustment for region will not be applicable for Japan sub-study. The nominal p-values for the mTSS-related endpoints in Japan sub-study should be interpreted with caution due to limited sample size.

Subgroup analysis for the primary endpoints is only applicable for global analysis as well. No subgroup analysis is planned for Japan sub-study due to limited sample size.

For radiographic data (i.e., mTSS-based endpoints), linear extrapolation will be applied to subjects who prematurely discontinued study drug or switched to a different study drug at Week 26, where the x-ray at the time point of interest after rescue switching or PD will be imputed assuming a linear relationship between baseline, the x-ray collected at rescue or PD, and the time point of interest. See Section 9.2.1.2 and Section 9.3.2 for details.

Missing Data Imputation Methods

To summarize the use of different missing data handling approaches in the analysis:

- For non-radiographic data: The NRI approach will serve as the primary analysis approach for binary endpoints in Period 1, while OC will be repeated as a sensitivity analysis for Week 12 key binary endpoints and AO will be repeated as a sensitivity analysis for Week 24 key binary endpoints. The MI approach will serve as the primary analysis approach for key continuous endpoints at Week 12 and 24.
- For radiographic data: Analysis based on both linear extrapolation and AO analysis will be conducted, and linear extrapolation results will be used for the purpose of multiplicity control.
- A missing not at random (MNAR) model that varies assumptions for the missing data in active treatment groups and MTX group may be used as a sensitivity analysis for key continuous endpoints to account for potential deviation from the MAR assumption.

Mixed Effect Model Repeat Measurement (MMRM) and Generalized Linear Mixed Model (GLMM) for Long-Term Analysis

The repeated measure analysis will be conducted using mixed model including As Observed measurements at all visits. MMRM will be used for continuous endpoints and GLMM will be used for binary endpoints. The mixed models will include the categorical fixed effects of treatment, visit and treatment-by-visit interaction, and stratification factor geographic region. For the MMRM analysis of change from baseline in continuous endpoints, the baseline measurement will be included as a continuous fixed covariate. The categorical fixed effect of subject's discontinuation status and other baseline covariates may also be included in the model as appropriate. Unstructured, Toeplitz, compound symmetry, or other covariance structures may be considered.

9.2 Efficacy Analysis for the Primary and Key Secondary Endpoints

9.2.1 Primary Efficacy Analysis

The primary endpoint for US/FDA regulatory purposes is the proportion of subjects achieving ACR50 response at Week 12. The primary endpoint for EU/EMA regulatory purposes is the proportion of subjects achieving Clinical Remission (CR) (defined by DAS28(CRP) < 2.6) at Week 24. For Japan/PMDA regulatory purposes, the primary endpoints are the proportion of subjects achieving ACR20 response at Week 12 and change from baseline in modified Total Sharp Score (mTSS) at Week 24. Analyses will be conducted separately for US/FDA, EU/EMA and Japan/PMDA regulatory purposes.

9.2.1.1 Analysis for ACR20, ACR50 and CR

For ACR20, ACR50 and CR, point estimate and 95% CI of the response rate for each randomized treatment group will be provided. Comparisons of the primary endpoint will be made between each Upadacitinib dose group and the MTX group using the Cochran-Mantel-Haenszel test adjusting for geographic region. Point estimate, 95% CI and p-value for the treatment comparison will be presented. Both nominal p-value constructed

using the Cochran-Mantel-Haenszel test and adjusted p-value through the graphical multiplicity procedure described in Section 9.2.5 will be provided. For the primary analysis, non-responder imputation (NRI) will be used. Subjects who meet the joint count rescue criteria at Week 16 or 20 will be treated as non-responders at Week 24 for the primary analysis.

9.2.1.2 Analysis for Change from Baseline in mTSS at Week 24

For mean change from baseline in mTSS at Week 24, both linear extrapolation and As Observed (AO) analyses will be conducted. Linear extrapolation results will be used for the purpose of multiplicity control.

According to protocol, subjects who prematurely discontinue study drug between \geq Week 12 and \leq Week 16 will have x-ray collected at the PD visit. All subjects who discontinued study drug but remained in the study through Week 24 will have another x-ray collected at the Week 24 visit. Available x-ray data will be assigned to the following analysis time points based on the analysis windows defined in Table 3: Baseline, Week 12, and Week 24.

In the linear extrapolation analysis, the Week 24 data will be imputed via linear extrapolation using baseline data and Week 12 data for subjects who prematurely discontinued study drug between Weeks 12 and 16, and for subjects with otherwise (i.e., not prematurely discontinued study drug prior to Week 16) missing observed x-ray at Week 24 window but have available x-ray in the Week 12 window.

In AO analysis, the observed Week 24 measurements will be used and attributed to the original randomized treatment groups regardless of study drug discontinuation.

To analyze the mean change from baseline in mTSS at Week 24, the point estimate and 95% CI will be reported for each randomized treatment group. Between-group comparisons for each Upadacitinib treatment group and the MTX group will be performed using ANCOVA model with treatment and geographic region as the fixed factors and the corresponding baseline value as the covariate. In the event that data severely deviates

from the normal distribution, non-parametric analyses such as the Wilcoxon rank sum test may be considered for treatment comparison.

Both nominal p-value and adjusted p-value through the graphical multiplicity procedure described in Section 9.2.5 will be provided.

9.2.2 Sensitivity Analysis of Primary Efficacy Variables

The analysis of ACR20 and ACR50 at Week 12 will be repeated using Observed Cases and the analysis of CR at Week 24 will be repeated using As Observed as a sensitivity analysis without any imputation. These analyses will be conducted on the FAS based on randomized treatment groups.

Supportive NRI analysis for ACR20, ACR50 and CR and supportive linear extrapolation and AO analysis for change from baseline in mTSS will also be conducted on the Per Protocol Analysis Set.

9.2.3 Key Secondary Efficacy Analyses

Ranked key secondary endpoints for US/FDA regulatory purposes are:

1. Change from baseline in DAS28 (CRP) at Week 12;
2. Change from baseline in HAQ-DI at Week 12;
3. Change from baseline in modified Total Sharp Score (mTSS) at Week 24;
4. Proportion of subjects achieving LDA based on DAS28 (CRP) ≤ 3.2 at Week 12;
5. Proportion of subjects achieving CR based on DAS28 (CRP) < 2.6 at Week 24;
6. Change from baseline in SF-36 PCS at Week 12;

Other key secondary endpoints for US/FDA regulatory purposes are:

1. ACR20 response rate at Week 12;
2. ACR70 response rate at Week 12;

3. Proportion of subjects with no radiographic progression (defined as change from baseline mTSS ≤ 0) at Week 24

Ranked key secondary endpoints at Week 24 for EU/EMA regulatory purposes are:

1. Change from baseline in DAS28 (CRP);
2. Change from baseline in HAQ-DI;
3. ACR50 response rate;
4. Change from baseline in modified Total Sharp Score (mTSS);
5. Proportion of subjects achieving LDA based on DAS28 (CRP) ≤ 3.2 ;
6. Change from baseline in SF-36 PCS;
7. Proportion of subjects with no radiographic progression at Week 24.

Other key secondary endpoints for EU/EMA purposes are:

1. ACR20 response rate at Week 24
2. ACR70 response rate at Week 24

Ranked key secondary endpoints for Japan/PMDA regulatory purposes are:

1. Change from baseline in DAS28 (CRP) at Week 12;
2. Change from baseline in HAQ-DI at Week 12;
3. Proportion of subjects achieving LDA based on DAS28 (CRP) ≤ 3.2 at Week 12;
4. Proportion of subjects achieving CR based on DAS28 (CRP) < 2.6 at Week 24;
5. Change from baseline in SF-36 PCS at Week 12.

Other key secondary endpoints for Japan/PMDA regulatory purposes are:

1. CR50 response rate at Week 12;
2. ACR70 response rate at Week 12
3. Proportion of subjects with no radiographic progression at Week 24

For Week 12 binary endpoints, similar NRI and OC analyses as for the primary endpoint of ACR20 and ACR50 at Week 12 will be conducted. For non-mTSS Week 24 binary endpoints, similar NRI and AO analyses as for the primary endpoint of CR at Week 24 will be conducted.

For the analysis of the proportion of subjects with no radiographic progression at Week 24, both linear extrapolation and AO analyses will be conducted (linear extrapolated and AO Week 24 mTSS data derived as described in Section 9.2.1.2). Linear extrapolation results will be used for the purpose of multiplicity control. Point estimate and 95% CI of the response rate for each randomized treatment group will be provided. Comparisons will be made between each Upadacitinib dose group and the MTX group using the Cochran-Mantel-Haenszel test adjusting for geographic region. Point estimate, 95% CI and p-value for the treatment comparison will be presented.

For all continuous key secondary endpoints other than mTSS, statistical inference will be conducted using analysis of covariance (ANCOVA) coupled with MI for missing data handling. Specifically, the ANCOVA model will include treatment and geographic region as the fixed factors and the corresponding baseline value as the covariates. The LS mean and 95% CI will be reported for each randomized treatment group; the LS mean treatment difference and associated 95% CI and p-value will be reported comparing each Upadacitinib dose group with the MTX group. For subjects who meet the rescue criteria at Week 16 or 20, data after rescue will be overwritten by last observation carried forward (LOCF).

Both nominal p-value and adjusted p-value through the graphical multiplicity procedure described in Section 9.2.5 will be provided.

9.2.4 Handling of Multiplicity

The overall type I error rate of the primary and ranked key secondary endpoints for the two doses in global analysis will be strongly controlled using a graphical multiple testing procedure [1]. Specifically, the testing will utilize the endpoint sequence of primary endpoint followed by the ranked key secondary endpoints in the order as specified in Section 9.2.3, and will begin with testing the primary endpoint using α of 0.025 for each dose. Continued testing will follow a pre-specified α transfer path which includes downstream transfer along the endpoint sequence within each dose as well as cross-dose transfer. Adjusted p-values for the primary and ranked key secondary endpoints will be provided based on the testing procedure.

The graphs for the testing procedures are provided in Figure 3 (for US/FDA regulatory purposes), Figure 4 (for EU/EMA regulatory purposes) and Figure 5 (for Japan/PMDA regulatory purposes). In the graphs, the arrows specify the α transfer paths. Once an endpoint is rejected (i.e., deemed significant) at its assigned significance level, its significance level will be transferred to subsequent endpoint(s) following the arrow(s). The numbers on the arrows denote the weights for transferring and (possibly) splitting significance levels. Specifically, the weight 1 denotes 100% transfer of significance level.

Figure 3. Graphical Multiple Testing Procedure for US/FDA Regulatory Purposes

[figure not shown]

Figure 4. Graphical Multiple Testing Procedure for EU/EMA Regulatory Purposes

[figure not shown]
[figure not shown]

Figure 5. Graphical Multiple Testing Procedure for Japan/PMDA Regulatory Purposes

9.2.5 Efficacy Subgroup Analysis

Non-mTSS primary efficacy endpoints will be examined in the subgroups listed in [Table 5](#) below. Treatment difference between each Upadacitinib dose and the MTX group will be presented with point estimate and 95% confidence interval using normal approximation. No p-value will be provided for subgroup analysis. If any of the resulting subgroups has fewer than 10% of the planned study size (i.e., < 90 subjects), the subgroup analyses for that variable will not be presented.

Table 5. Subgroups for Efficacy Analysis

Subgroup Factor	Categories
Age	< 40, [40, 65), ≥ 65
Sex	Male or Female
Weight	< 60 kg or ≥ 60 kg
BMI	< 25 or ≥ 25
Race	White, Black or African American, American Indian or Alaska Native, Native Hawaiian or Other Pacific Islander, Asian, Other
Geographic Region	North America, South/Central America, Western Europe, Eastern Europe, Asia/Other
RA disease duration from diagnosis	< 6 months or ≥ 6 months
Baseline Rheumatoid Factor Status	Positive or Negative
Baseline Anti-CCP Antibody Status	Positive or Negative
Baseline both RF positive and Anti-CCP positive	Both Positive vs At Least One Negative
Baseline both RF negative and Anti-CCP negative	Both Negative vs At Least One Positive
Baseline DAS28[hsCRP]	≤ 5.1 or > 5.1

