### **8.1.4.1 Efficacy Analysis for Period 1**

#### **8.1.4.1.1 Primary Efficacy Variables**

The primary endpoints for US/FDA, EU/EMA, and Japan/PMDA regulatory purposes are listed in Section 5.3.3.1.1. Analyses will be conducted separately for US/FDA, EU/EMA and Japan/PMDA regulatory purposes; for each set of analyses, only the specified primary endpoint is applicable.

The analysis of the primary efficacy endpoint will be conducted on the FAS based on treatment as randomized. Supportive analysis will also be conducted on the Per Protocol Analysis Set. For the analysis of ACR20, ACR50 and CR, the comparisons will be made between each upadacitinib dose and the MTX group using the Cochran-Mantel-Haenszel test adjusting for main stratification factors. Non-Responder Imputation (NRI) will be used as the primary analysis. For the analysis of change from baseline in mTSS, between-group comparisons for each upadacitinib treatment group and the MTX treatment group will be performed using the analysis of covariance model with treatment group as the fixed factor, and the corresponding baseline value and the main stratification factors as the covariates. Both linear extrapolation analysis and as observed analysis will be conducted.

The primary efficacy analyses will be performed in demographic subgroups including age, gender, weight, body mass index, race, and geographical region to assess the consistency of the treatment effect. Additional subgroup analyses based on baseline disease characteristics and stratification factors will also be conducted.

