4.2 Overall Study Design and Plan

This is a Phase 3 multicenter study that includes two periods and a Japan sub-study. Period 1 is a 48-week randomized, double-blind, parallel-group, active comparator controlled treatment period designed to compare the safety and efficacy of Upadacitinib 7.5 mg QD monotherapy (for subjects in Japan only), 15 mg QD monotherapy, and 30 mg QD monotherapy versus MTX monotherapy in adult MTX-naïve subjects with moderately to severely active RA. Period 1 is also designed to compare the efficacy of Upadacitinib 15 mg QD monotherapy and 30 mg QD monotherapy versus MTX monotherapy for the prevention of structural progression. Period 2 is a long-term extension to evaluate the long-term safety, tolerability, and efficacy of Upadacitinib (7.5, 15, or 30 mg QD) in subjects with RA who have completed Period 1. Starting with Amendment 5.01.01, subjects in Japan receiving upadacitinib 30 mg QD will be switched to upadacitinib 15 mg QD. For other countries, starting with Amendment 6, subjects receiving upadacitinib 15 mg and 30 mg QD will receive open label upadacitinib 15 mg QD and subjects receiving MTX will receive open label MTX.

The study is designed to enroll approximately 975 subjects at approximately 330 study centers worldwide to meet scientific and regulatory objectives without enrolling an undue number of subjects in alignment with ethical considerations. Therefore, if the target number of subjects has been enrolled, there is a possibility that additional subjects in screening may not be enrolled.

The study duration includes a 35-day screening period, a 48-week randomized, double-blind, parallel-group, active-comparator controlled treatment period (Period 1); a 212 week long-term extension period (blinded until the last subject completes the last visit of Period 1) (Period 2); and a 30-day follow-up (call or site visit).

Subjects will be randomized in a 1:1:1 ratio to treatment Groups 2, 3 and 4 below, except for subjects from Japan, who will be randomized in a 2:1:1:1 ratio to Groups 1, 2, 3 and 4:

- Group 1: Upadacitinib 7.5 mg QD monotherapy (subjects in Japan only; N = 75)

- Group 2: Upadacitinib 15 mg QD monotherapy (N = 300) (includes 37 subjects from Japan)
- Group 3: Upadacitinib 30 mg QD monotherapy (N = 300) (includes 37 subjects from Japan)
- Group 4: MTX monotherapy (N = 300) (includes 37 subjects from Japan)

Randomization is stratified by geographic region.

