4.3 Sample Size

The planned sample size of 900 (not including the Japan-specific upadacitinib 7.5 mg QD treatment group) provides at least 90% power for a 20% difference in ACR50 response rate (assuming a Week 12 MTX ACR50 response rate of 20%). This sample size also

provides at least 90% power for a 16% difference in DAS28 CR response rate (assuming a Week 24 MTX CR response rate of 24%), and for a 20% difference in ACR20 response rate (assuming a Week 12 MTX ACR20 response rate of 50%). With this sample size, there is approximately 80% power to detect a difference of 0.58 in change from baseline in mTSS (assuming a standard deviation of 2.2). This sample size will also provide at least 90% power for other ranked key secondary endpoints including change from baseline in DAS28 (CRP), change from baseline in HAQ-DI, ACR70, and SF-36. The above power calculations are all based on a two-sided significance level of 0.025 and accounting for a 10% dropout rate. An additional 75 Japanese subjects will be enrolled into the Japan-specific upadacitinib 7.5 mg QD treatment arm for Japan/PMDA regulatory purposes.

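### The SAP's subgroup size rule withholds a whole variable when any one level has under 90 subjects, so one sparse race level would also remove the large ones

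*SAP*

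**What the plan says.** Protocol 8.1.4.1.1 makes the commitment: "The primary efficacy analyses will be performed in demographic subgroups including age, gender, weight, body mass index, race, and geographical region", with the stated aim of judging whether the treatment effect is consistent. It sets no levels, minimum size or form of display.

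SAP 9.2.5 implements this for the primary endpoints other than mTSS. Table 5 gives the levels. For race they are "White, Black or African American, American Indian or Alaska Native, Native Hawaiian or Other Pacific Islander, Asian, Other". The size rule has two parts:

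- Trigger: "If any of the resulting subgroups has fewer than 10% of the planned study size (i.e., < 90 subjects".
- Consequence: "the subgroup analyses for that variable will not be presented".

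Section 9.2.5 has no rule for pooling small levels and no option to leave out only the small one. Results are point estimates with 95% confidence intervals and no p-values. SAP 9.1 limits the scope: "Subgroup analysis for the primary endpoints is only applicable for global analysis as well".

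**The concern.** A minimum size protects the reader from unstable estimates in small groups. Here the trigger is any single level, while the consequence falls on the whole variable. A race level with a handful of subjects would therefore withhold the White and Asian results, however many subjects those levels contain.

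Race is the most exposed variable because it has six levels, several of which could be small. Age (three levels) and region (five levels) come under the same rule. What is at stake is the report on consistency of effect across the larger groups, which is the purpose the protocol gives for these analyses.

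**Working it through.** **Inputs**

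- Planned size of the global analysis: 900, three arms of 300 (SAP 4.2 and 4.3).
- Limit: 10% of planned size, stated as 90 (SAP 9.2.5).
- Race levels: 6 (SAP Table 5).
- Japan subjects: 37 in each of the three global arms (SAP 4.2).
- Race distribution: not given in either document, so shares below are assumptions and a range is shown.

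**1. Reproduce the limit.** 0.10 × 900 = 90, which matches. (10% of all 975 subjects would be 97.5, so the base is the global analysis.)

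**2. What the rule requires for race.** If all six levels must pass, 6 × 90 = 540 subjects are fixed by the rule, and 540 / 900 = 60%. The Japan subjects in the global arms number 3 × 37 = 111. If they are all recorded as Asian (an assumption), that level passes, but the other five still need 5 × 90 = 450 of the remaining 900 − 111 = 789.

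**3. Chance that one level reaches 90.** With X ~ Binomial(900, p), P(X ≥ 90) is:

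| Assumed true share p | Expected count | P(X ≥ 90) |
|---|---|---|
| 1% | 9 | 2 × 10⁻⁵⁸ |
| 2% | 18 | 6 × 10⁻³⁵ |
| 5% | 45 | 7 × 10⁻¹⁰ |
| 8% | 72 | 0.018 |
| 9% | 81 | 0.16 |
| 10% | 90 | 0.52 |
| 12% | 108 | 0.97 |

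Race cannot be shown unless every level passes, so one level at 8% or less caps the chance at 0.018.

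**4. Chance that all six pass** (multinomial simulation, 200,000 draws per mix):

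- Mixes tried with at least one level at 5% or less: 0 draws passed.
- One level at 50%, five at 10%: 1.5%.
- One level at 40%, five at 12%: 87%.
- Six equal levels: essentially 100%.

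**5. Empty levels.** The rule speaks of resulting subgroups, which could mean only levels that occur. A level then also passes by having no subjects, with probability (1 − p)^900. At p = 0.5% this is 0.995^900 ≈ 0.011, still under 2%. Below that share it matters more. With shares of 87%, 12.65%, 0.2% and three levels at 0.05%, race is shown in 4.3% of draws, against none when an empty level counts as failing. On this reading the 2% bound holds for a level with a share from about 0.5% to 8%.

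**6. The SAP's own practice on region.** SAP 6.1 lists seven baseline regions, with Japan, the rest of Asia and Other separate. Table 5 merges these last three, leaving five. Race goes from 6.1 to Table 5 with all six levels unchanged.

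**The case against.** The strongest points on the other side are these.

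- **The analysis is finished.** SAP 11.1 says the primary efficacy analysis and Period 1 reporting were completed under version 2.0, and that version 3.0 governs only later long-term reporting. The long-term plan in SAP 9.4 has no subgroup component. This stands: a new table would be a post hoc supplement. The version 3.0 change list does not mention 9.2.5, so the rule was probably already in version 2.0, but the documents do not show that text.
- **Performing is not presenting.** A reader might infer that the SAP cancels an analysis the protocol promises. The text does not go that far. The protocol says the analyses will be performed, Protocol 8.1 leaves detail to the SAP, and the SAP limits only what is displayed. The conflict is one of reporting. Even so, an assessment of consistency that nobody sees does not serve its stated purpose.
- **The race mix is unknown.** A reader might also infer that race is almost certain never to appear, or that it was in fact suppressed. Neither document gives a race distribution or any results, so only the conditional statement is supported. For age and region there is likewise no distribution, only the same mechanism.
- **The consequence is small.** The subgroups carry no p-values and do not enter the graphical testing procedure or the sample size. This stands.
- **A size limit avoids unstable estimates and selective display.** It does: 90 subjects at 1:1:1 allocation is 90 / 3 = 30 per arm. That is a reason to withhold a level below the limit. It is no reason to withhold levels that meet it, and a fixed count-based rule applied level by level is equally protected against selective display.

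**Conclusion.** The point holds as a defect in the wording of the rule. As written, one race level with 1 to 89 subjects removes every race result, and the consistency assessment in Protocol 8.1.4.1.1 goes unreported for that variable. If one level has an assumed share of 8%, the chance that race is shown is below 2%, and it is lower still at smaller shares, provided that an empty level counts as failing; if empty levels are ignored, the bound applies from about 0.5% upward. Race would be likely to appear only if every level that occurs made up more than about a tenth of the trial.

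The same mechanism could remove age or region if one level is small, but nothing in the documents lets that be quantified. The effect is confined to descriptive reporting: no primary or ranked secondary conclusion depends on it. The point is worth correcting, at modest priority.

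**What to change.** 1. Check whether race, age or region was suppressed in the Period 1 report because one level was below 90.
2. If so, add a table for that variable, labelled as post hoc because it follows unblinding. Show each level with at least 90 subjects and pool the sparse levels into one remainder (for race, for example, White / Asian / all other). Form the groups from counts alone, not from results. Give estimates and 95% CIs only.
3. Correct the sentence in SAP 9.2.5 so that the 90-subject limit applies to levels: levels that meet it are presented, sparse levels are pooled, and a remainder still below 90 is withheld alone, with its count stated. State whether empty levels count.

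The cost is one sentence and at most one table per suppressed variable. Since no subgroup p-values are planned, there is no type I error cost. The drawback is that a pooled level is less specific and mixes groups that may have little in common; the choice of pooling is a judgement that the documents do not settle.
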